To address **Specific Aim 1**, we will use a prospective, parallel-group, repeated-measures design to compare behavioral, physiological, and biochemical (plasma ORX) responses in 2 independent, unmedicated groups of PD outpatients (n=6 in each group) at baseline/resting state and after panic provocation due to brief (1 minute) inhalation of a 35% CO₂ / 65% O₂ gas mixture. PD patients will be randomized, in a double-blind manner, to receive either a single, oral dose of the mixed ORX1/2 receptor antagonist, suvorexant (10 mg dose), or identical placebo, 120 minutes before CO₂ challenge.

Exploratory aim: To acquire DNA samples for future candidate gene/DNA analysis. Genes of interest with respect to ORX metabolism are the preproORX gene and genes that code for the receptors ORX1 and ORX2.

Expected results: It is expected that, compared to placebo, suvorexant pretreatment will blunt behavioral, physiological, and biochemical (plasma ORX) responses to 35% CO₂ in PD, due to suppression of CNS ORX hyperactivity. The effect sizes generated from the pilot work will permit planning and powering of a larger-scale study, to definitively address Specific Aim 1.

INNOVATION

The current work promises to determine the human applicability of a novel pathophysiologic concept generated from preclinical science, in this instance the ORX hyperactivity hypothesis of panic/anxiety. Our proposed study will perform rapid clinical testing of the ORX hypothesis with a view to identifying a new class of anxiolytic agents (ORX1 antagonists).¹⁵

This translational, experimental medicine approach is expected to hasten proof-of-concept testing of novel anxiolytics for PD and for all anxiety syndromes where panic attacks are an important clinical feature. Not only does the ORX hyperactivity hypothesis promise to inform new treatment development, but it may also shed light on therapeutic mechanisms of standard antipanic treatments, such as SSRIs.²⁴ In addition, ascertainment of the utility of plasma ORX as a biomarker of illness state and clinical improvement could immediately impact practice.

Furthermore, such a finding may well have future transdiagnostic implications with regard to the pathogenesis of panic symptoms that occur in a variety of psychiatric syndromes (e.g., other anxiety disorders, trauma-related disorders) and in medical disorders with panic as a component, such as chronic obstructive pulmonary disease and chronic asthma.

Public Health Impact of the Project

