Patient Selection and Preliminary Evaluation (Study Visit 1—Screening Visit)

Patients between the ages of 18 and 65 years will be admitted to the study after they have given their written informed consent to participate. Study participants will also be given the choice whether to give their additional written informed consent to provide a blood sample for future DNA analysis.

Patients will undergo a complete medical and psychiatric evaluation by a study doctor assisted by the appropriate study/hospital staff (see Table 2), including history taking, physical examination, diagnostic interview, electrocardiogram, laboratory tests (comprehensive metabolic panel, CBC, free T4, urine pregnancy test, urinalysis), urine toxicology screen, and urine pregnancy test in women of child-bearing potential.

Inclusion criteria: To participate in the study, patients must meet the following inclusion criteria:

- Men and women between the ages of 18 and 65 years are eligible for inclusion in this study.
- They must be in stable physical health as determined by a medical evaluation (see Table 2), including physical examination, electrocardiogram, laboratory findings (comprehensive metabolic panel, CBC, free T4, urine pregnancy test, urinalysis), urine toxicology screen, and a negative urine pregnancy test in women of child-bearing potential.

- They must satisfy the new DSM-5 clinical criteria for a current principal diagnosis of PD³⁸ as confirmed by a semi-structured, diagnostic interview, the MINI,³⁹ administered by the PI, [name].
- Since clinical depression (MDD) is associated with CSF ORX abnormalities,⁴⁰ only patients with a current PD without MDD will be enrolled. They will also be required to have a current Montgomery-Asberg Depression Rating Scale (MADRS) total score <12.⁴¹
- They will be off all regular psychiatric medications and avoid drinking grapefruit juice for at least 2 weeks prior to the 35% CO₂ test.
- They must not be pregnant or breastfeeding a baby; and women of childbearing potential must be using birth control while on this study.

Exclusion criteria: The following is a list of the exclusion criteria in reference to this study:

- any history of a psychotic disorder, bipolar disorder, MDD, depression NOS, obsessive compulsive disorder, an eating disorder, post-traumatic stress disorder, or generalized anxiety disorder
- medical conditions for which suvorexant could be contraindicated, such as narcolepsy
- any other sleep disorder⁴²

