- a substance use disorder, as defined by the DSM-5, within 6 months of the screening visit
- ongoing use of psychiatric medications in the 2 weeks prior to the 35% CO₂ test
- current use of certain drugs,⁴³ including
 - strong CYP3A inhibitors (such as ketoconazole, itraconazole, posaconazole, clarithromycin, nefazodone, ritonavir, saquinavir, nelfinavir, indinavir, boceprevir, telaprevir, telithromycin, and conivaptan);
 - moderate CYP3A inhibitors (such as amprenavir, aprepitant, atazanavir, ciprofloxacin, diltiazem, erythromycin, fluconazole, fosamprenavir, imatinib, verapamil);
 - strong CYP3A inducers (such as rifampin, carbamazepine and phenytoin);
 - digoxin
- history of any neurological disorder affecting the CNS
- history of uncontrolled or serious medical illness
- a history of hypersensitivity or allergy to suvorexant
- pregnancy or lactation status, or unwillingness to use birth control while on this study, for women of child-bearing potential

- compromised lung function (e.g., COPD, emphysema, idiopathic pulmonary fibrosis, lung cancer)
- inability to fast the required amount of time prior to study visit 2
- a positive test for cannabinoids, opiates, benzodiazepines, amphetamines, cocaine and metabolites
- out-of-range lab values
- an abnormal EKG
- a score > 12 on the Montgomery-Asberg Depression Rating Scale (MADRS)
- inability or unwillingness to avoid drinking grapefruit juice for two weeks prior to the 35% CO₂ challenge test
- a history of sudden onset of muscle weakness (cataplexy)

Notes regarding the urine toxicology tests and benzodiazepine screening: The purpose of the urine screening is twofold: (1) study validity (patients are excluded if the screening reveals use of certain substances, when by history patients have denied taking); (2) patient safety (the sedative effects of the study drug and a controlled substance, such as a benzodiazepine or pain medicine, could be additive). Substances screened for include cannabinoids, opiates, benzodiazepines, amphetamines, cocaine, and metabolites.

If the PI believes that any subjects are a “borderline case” for inclusion / exclusion, he will discuss the issue with the Safety Monitor or the patient’s primary care doctor, as appropriate.

TABLE 2: STUDY PLAN & SCHEDULE OF ACTIVITIES

Visit	1 Screening (2 hr)	2 CO ₂ Test visit (3.5 hrs)	3 Follow-up (exit) visit (0.5 hr)
Days/Weeks		About 1 week after visit 1	About 1 week after visit 2
Informed consent – orexin study	X		

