Informed consent – DNA sample	X		
Psych Hx/Diagnosis Interview/MINI	X		
Inclusion/exclusion criteria	X		
Medical history	X		
Physical examination	X		
Vital signs	X	X (pre-, during, and post-CO ₂)	
ECG	X		
Comprehensive metabolic panel; CBC w/diff; free T4	X		
Urine pregnancy test (females)	X		
Urinalysis	X		
Urine toxicology screen	X		
Urine benzo screen		X	
SUVOREXANT 10MG/PLACEBO.		X (120 mins pre CO ₂)	
OREXIN LEVELS		X (pre-, during & post- CO ₂ challenge)	
DNA sample (optional: obtained only if additional consent form is signed)		X	
PDSS/CGI clinical scales		X (completed by a study doctor pre-CO ₂)	
Visual Analog Scales (Anxiety) and Panic Symptoms Scale (PSS)		X (completed by subjects pre-, during, and post-CO ₂)	
Interview with MD to verify return to baseline			X

Referral to appropriate doctor to treat panic (if desired)			X
--	--	--	---

35% CO₂ Inhalation Test Procedures (Study Visit 2, see Table 3)

After the screening visit (visit 1), patients will be scheduled in about 1 week for the CO₂ challenge test (study visit 2), which will take place in an exam room in East Medical Plaza (University Neurology Associates).

Upon arrival for study visit 2, each participant will receive a consecutive study code. The master list of study codes will be linked with a random assignment of suvorexant and placebo. The randomization schedule will be generated by [name], using a computer program. The pharmacy will maintain an independent list of the study codes and randomization assignments (to either 10mg suvorexant or placebo).

The following instruments will be used by the PI or sub-I to assess baseline PD clinical severity just prior to the CO₂ test:

- the Clinician's Global Impressions of severity of illness (CGI-S)⁴⁴
- the Panic Disorder Severity Scale (PDSS)⁴⁵

The following instruments will be administered to subjects at baseline and serially throughout the test:

- a change-sensitive, patient-rated, Vertical Analog Scale (VAS) mood ratings (5 mood states including fear, nervousness, anxiety, rated 0-100)⁴⁶
- a Patient Panic Symptom scale (PSS; 27 items, each rated 1-4)⁴⁶

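### Do the two-week medication and grapefruit-juice restrictions go unchecked in the week between screening and the CO₂ test?

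*Combined protocol and SAP*

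**What the plan says.** Three eligibility statements in the protocol run up to the CO₂ test:

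- Inclusion criteria: "They will be off all regular psychiatric medications and avoid drinking grapefruit juice for at least 2 weeks prior to the 35"% CO₂ test.
- Exclusion criteria, medication: "ongoing use of psychiatric medications in the 2 weeks prior to the 35"% CO₂ test.
- Exclusion criteria, juice: "inability or unwillingness to avoid drinking grapefruit juice for two weeks prior to the 35"% CO₂ challenge.

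The test takes place at visit 2, which Table 2 sets at "About 1 week after visit 1". The text under 35% CO₂ Inhalation Test Procedures gives the same interval.

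Table 2 marks the row "Inclusion/exclusion criteria" at visit 1 only. The psychiatric interview, the medical history and the full urine toxicology screen are also marked at visit 1 only. At visit 2 the one item on drug use is "Urine benzo screen".

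Allocation also happens at visit 2: "Upon arrival for study visit 2, each participant will receive a consecutive study code", and the code list is linked to the random assignment. Specific Aim 1 describes the comparison as one between "2 independent, unmedicated groups of PD outpatients (n=6 in each group").

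**The concern.** A criterion about conduct up to the test day cannot be fully confirmed a week earlier. At visit 1 the doctor can establish what the patient has done so far; the remaining days are only an intention. The visible visit 2 steps do not clearly close that gap. The timeline opens with ratings, vital signs and an orexin sample, and Adverse Events/Safety Monitoring adds a pre-dose check that the patient has an escort. A benzodiazepine screen cannot show other psychiatric medication or grapefruit juice.

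The stake would be a patient who resumed a regular psychiatric drug between the visits and was then allocated, dosed and analysed as unmedicated. The protocol's rationale for CO₂ inhalation says the challenge can track improvement on antipanic drugs, so the outcome is described as sensitive to the very medication in question. The groups are small, and their effect sizes are meant to inform a larger study. Methods for unblinding the study also calls for documented decisions on whether each subject's data can be evaluated, and for that week the visible plan supplies only a benzodiazepine result.

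**Working it through.** **The plan's own timeline.** Table 2 gives about 7 days from visit 1 to visit 2 and about 7 days from visit 2 to visit 3. The sum, 7 + 7 = 14 days, matches the roughly two weeks of participation stated under Follow-up Contacts. The 7-day gap is therefore what the protocol intends.

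**Days after the visit 1 review.** The restricted window is 14 days ending at visit 2. The share falling after visit 1 is (visit gap) / 14:

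- gap of 7 days: 7/14 = 50%
- gap of 5 days (assumed lower end of *about 1 week*): 5/14 = 36%
- gap of 10 days (assumed upper end): 10/14 = 71%

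**Weight of one patient.** 1/6 = 16.7% of an arm; 1/12 = 8.3% of the study. These fractions hold for any single-patient problem in a trial of this size and say nothing about how likely this one is.

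**Do the window and the visit interval conflict?** Take the 7-day gap.

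- Already abstinent for 7 days at visit 1: 7 + 7 = 14 days at the test. The criterion is met.
- Stops only at visit 1: 0 + 7 = 7 days at the test, short of 14. The criterion is not met and the patient is ineligible on that schedule.

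The criterion sorts both patients correctly. The two weeks of participation cover visits 1 to 3 and do not describe the washout, so nothing needs reconciling.

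**What the criteria cover.** The inclusion wording concerns *regular* psychiatric medication and the exclusion concerns *ongoing* use. A breach therefore means starting or resuming regular use within about a week of a screening at which the patient was off it. An isolated dose is not clearly a breach. The juice exclusion concerns ability and willingness, which can be judged in advance at screening. Only the inclusion criterion makes actual juice intake in that week a matter of eligibility.

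**What visit 2 provides.**

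- The benzodiazepine screen is itself an eligibility re-check, because a positive result is an exclusion criterion. Its clock time is not stated. The notes on toxicology testing give additive sedation with the study drug as one purpose, which makes sense only if the result is read before dosing.
- The principal investigator or a sub-investigator rates panic severity (PDSS and CGI-S). The timeline puts this at −130 minutes, 10 minutes before the capsule, and a study doctor is present when it is taken.
- Table 2 and the visit 2 timeline do not list everything. Table 2 has no row for the MADRS, for the escort check or for the fast required before visit 2, although all three are required elsewhere in the protocol. A missing row is weak evidence of a missing check.

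**Direction of any error.** Medication or juice taken between the visits precedes issue of the study code, and treatment is double-blind. It therefore cannot depend on the assigned arm. It could add noise or fall unevenly by chance with six per group, but it is not a mechanism that systematically favours one arm.

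**The case for a change.** The strongest case for a change is that the fix is nearly free: one row in Table 2 and one form entry at visit 2, with no effect on any clinical rule. The sponsor already accepts that drug use between visits needs checking, since it repeats one test, and that test covers a single drug class. The weekly data review and the compliance meeting under Data Management look at data already collected, so they cannot stop an ineligible patient being dosed. The protocol also cites an open study of CO₂ reactivity after one week of citalopram; going by its title alone, the unchecked interval is about as long as that treatment period.

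Much of this stands as fact. No recorded medication or juice question at visit 2 is visible, the benzodiazepine screen is narrow, and an informal question from the doctor is likely but not documented. The case reports, however, a missing confirmation and not a wrong rule. It does not show that any patient would break the restriction, how many might, or what that would do to a result. The case report forms are not available, so the confirmation may already be on them.

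**Conclusion.** No change to the plan follows. The day count is right: about 7 of 14 restricted days (36% to 71% under the assumed 5 to 10 day gap) come after the visit 1 review, and the only re-check visible at visit 2 is for benzodiazepines. But both medication criteria, and the inclusion criterion on juice, already bind up to the CO₂ test. Followed as written, they admit only eligible patients. What is missing is an explicit schedule line for a question that staff meeting the patient before dosing would sensibly ask, and whose answer would be available to the blinded evaluability decisions. Writing it down would be tidy record-keeping; it would not alter the eligibility rules, the allocation, the outcomes or the analysis of this pilot.

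This rests on three assumptions: that the study doctor who rates each patient before dosing applies the criteria as they stand on that day, that the benzodiazepine result is read before the capsule is given, and that a breach, if found, is judged under the existing criteria while the code is still closed. Nothing in the documents contradicts any of them.

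### On the dosing day only benzodiazepines are tested for, although the plan's safety reason for urine screening also names pain medicine; opiate use since visit 1 is not tested for

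*Combined protocol and SAP*

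**What the plan says.** The notes on urine testing under the exclusion criteria give two reasons for it. The first is validity: "patients are excluded if the screening reveals use of certain substances, when by history patients have denied taking". The second is safety: "patient safety (the sedative effects of the study drug and a controlled substance, such as a benzodiazepine or pain medicine, could be additive"). They then list the panel: "Substances screened for include cannabinoids, opiates, benzodiazepines, amphetamines, cocaine, and metabolites". One exclusion criterion is "a positive test for cannabinoids, opiates, benzodiazepines, amphetamines, cocaine and metabolites", with no visit attached.

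Table 2 has two separate urine drug rows. "Urine toxicology screen" is marked at visit 1 only and "Urine benzo screen" at visit 2 only. The row "Inclusion/exclusion criteria" is also marked at visit 1 only, as is medical history. Visit 2 is scheduled "About 1 week after visit 1" and is the day on which study drug is given.

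The minute-by-minute visit 2 timetable starts at -130 minutes with ratings, vital signs and an orexin blood draw, followed by the dose at -120 minutes. It contains no urine step.

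**The concern.** Additive sedation with the study drug can arise only once the study drug has been taken, so the test that serves this purpose best is the one closest to dosing. On that day the plan tests for one of its two named examples and not the other. Repeating the benzodiazepine test suggests that a week-old negative was not thought sufficient for that class. The documents do not say why it is sufficient for opiates.

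Two things are at stake. On safety, a patient who takes an opiate pain medicine between the visits could receive suvorexant without any scheduled check for the combination that the plan itself flags. On validity, undeclared opiate, stimulant or cannabinoid use could plausibly alter the anxiety ratings and vital signs recorded around the CO₂ challenge. The trial has 6 patients per group, and its effect sizes are meant to plan a larger study.

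**Working it through.** No formula applies and the plan gives no figure to reproduce. The check sets the stated purposes beside the schedule.

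| Class on the panel | Visit 1 | Visit 2 (dosing) | Purpose most directly served |
|---|---|---|---|
| Benzodiazepines | tested | tested | safety (named) and validity |
| Opiates | tested | not tested | safety (as pain medicine) and validity |
| Cannabinoids | tested | not tested | mainly validity |
| Amphetamines | tested | not tested | validity |
| Cocaine | tested | not tested | validity |

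1. **Coverage.** Visit 1 covers 5 of 5 classes and visit 2 covers 1 of 5, so 5 - 1 = 4 are not re-tested. The interval is about 1 week.
2. **Which purpose is affected.** Of those 4, the quoted sedation reason points chiefly to one, opiates. This takes pain medicine to correspond to the opiate class, which is the natural reading but an inference. The other three matter mainly for validity.
3. **Other controls on opiates.** The barred medications are psychiatric drugs in the 2 weeks before the CO₂ test, strong and moderate CYP3A inhibitors, strong CYP3A inducers, and digoxin. Benzodiazepines taken as regular psychiatric treatment fall under the first. Opiate pain medicine is not named in any of them, so the urine panel is the only control specific to that class.
4. **Other checks at visit 2.** Table 2 has no eligibility re-check, history update or concomitant-medication review there. A patient could volunteer recent use, but no question is scheduled, and the validity reason presumes that some patients deny use.
5. **Order of events on the day.** The section on the CO₂ test procedures assigns each patient a consecutive study code on arrival at visit 2, and that code is linked to the random assignment. The timetable leaves -120 - (-130) = 10 minutes between the first listed activity and the dose, with no urine step. So even the existing benzodiazepine result has no stated place before code assignment or before dosing.

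**The case against.** The strongest reply is that this is a deliberate two-tier screen. The note's heading refers to toxicology tests and benzodiazepine screening separately, and Table 2 schedules those same two tests. The 2-week ban on psychiatric medication runs past visit 1, and benzodiazepines are the listed class that panic patients would most plausibly take as treatment, so re-testing them alone is coherent. This reading is plausible and part of it stands: nothing in the protocol promises a full panel at visit 2, and a reader who infers a broken commitment goes too far. But the protocol does not state this reasoning, and it does not cover opiates.

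The second reply is that the residual risk is already narrowed. Patients with a substance use disorder in the 6 months before screening are excluded, and those enrolled have a negative five-class panel from about a week earlier. A study doctor is present when the dose is taken, the coordinator stays until the CO₂ test, and both are present from then until discharge. Driving home is barred, an escort stays until 7 hours after dosing, and a call follows the next day. This stands as mitigation of harm. None of it tests for use or protects the measurements.

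Three further inferences are tempting and not supported:
- That opiate use would necessarily go undetected. It is not tested for, but disclosure or clinical observation remains possible.
- That all four untested classes are a sedation hazard under the plan's own reasoning. It names only benzodiazepines and pain medicine.
- That one affected patient, 1/6 = 17% of a group, measures the bias. That fraction holds for any irregularity in any patient and says nothing about how often this one occurs or what it does to the results.

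**Conclusion.** The point holds as a cheap improvement. The schedule is narrower than the purpose given for it: opiates, the second sedation risk the plan names, are not tested for in the week or so before dosing. Three further classes are not re-tested, which is mainly a validity matter.

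Its size cannot be put as a number. The documents give no frequency of interim use, and no effect on any planned comparison has been shown. The conclusion rests on reading Table 2's columns as printed, on taking pain medicine to mean the opiate class, and on no unlisted medication check taking place at visit 2. If such a check is already routine, part of the safety gap closes, but the gap in detecting denied use does not.

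**What to change.** Reconcile Table 2 and the visit 2 timetable with the stated purposes of screening:

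- In Table 2, replace the benzodiazepine-only test at visit 2 with the visit 1 panel, or at minimum add opiates to it. It can be run on the urine that the existing row already requires.
- Add the urine step to the visit 2 timetable, so that the result is read before the study code is assigned and before the dose at -120 minutes.
- State that the existing positive-test exclusion applies at that point. No new eligibility rule is needed, since the criterion names no visit. Applying it before the code is given means that no patient already linked to an arm is excluded because of the result.

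The costs are modest. The test is slightly dearer for about 2 × 6 = 12 patients. The pre-dose period lengthens, because the present 10 minutes already hold the ratings, vital signs and blood draw. An occasional patient is lost at visit 2. Recruitment of 1-2 patients a month over 8 months gives 8 × 1 = 8 to 8 × 2 = 16 patients against the 12 needed, so each such loss has some recruitment cost.

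### The five-class urine screen is run only at visit 1; the dosing-day test covers benzodiazepines alone, which falls short of the protocol's own stated purposes for screening

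*Combined protocol and SAP*

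**What the plan says.** All places are in the combined protocol and SAP.

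- **Exclusion criteria.** One criterion is "a positive test for cannabinoids, opiates, benzodiazepines, amphetamines, cocaine and metabolites". It names no visit.
- **Note on urine toxicology and benzodiazepine screening**, after the exclusion list. It gives two purposes. The first is study validity: "patients are excluded if the screening reveals use of certain substances, when by history patients have denied taking". The second is patient safety: "the sedative effects of the study drug and a controlled substance, such as a benzodiazepine or pain medicine, could be additive". It then states the coverage: "Substances screened for include cannabinoids, opiates, benzodiazepines, amphetamines, cocaine, and metabolites". It does not say which test, or which visit, covers which class.
- **Table 2, schedule of activities.** The row "Urine toxicology screen" is marked at visit 1 only. The row "Urine benzo screen" is marked at visit 2 only. The row "Inclusion/exclusion criteria" is marked at visit 1 only, as is medical history. Visit 2 is timed as "About 1 week after visit 1".
- **Visit 2 timeline (Table 3).** The patient arrives at -130 minutes and takes the capsule at -120 minutes. No urine test and no repeat eligibility check appears before the capsule.

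**The concern.** Both purposes in the note depend on what is in the patient's body when the capsule is taken and the CO₂ is inhaled. A screen about a week earlier cannot establish that. By adding a urine test on the dosing day, the plan appears to accept this for benzodiazepines, but it leaves out the other four classes it lists. One of those is opiates, the listed class closest to the pain-medicine example that the note itself uses for additive sedation.

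Two things are at stake. On safety, a patient randomised to suvorexant could take it with a sedating substance that the screening was meant to find. On validity, an undetected substance could alter the behavioural and physiological responses in either arm. The pilot exists to supply effect sizes for a larger study, and each arm has only six patients.

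**Working it through.** The plan gives no figure on this point to reproduce. The check is a comparison of sections and a count.

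**1. Classes covered, by visit**

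| Class | Exclusion list and note | Visit 1 urine | Visit 2 urine (dosing day) |
|---|---|---|---|
| Benzodiazepines | yes | yes | yes |
| Opiates | yes | yes | no |
| Cannabinoids | yes | yes | no |
| Amphetamines | yes | yes | no |
| Cocaine | yes | yes | no |

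Five classes are listed and one is tested on the dosing day, so 5 − 1 = 4 are not. The visit 1 column takes the toxicology screen in Table 2 to be the five-class test that the note describes. No other test in the schedule fits that description.

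**2. Does another section close the gap?**

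- The two-week restriction before the CO₂ test concerns psychiatric medications. It does not name opiates or cannabis.
- The list of prohibited concomitant drugs covers CYP3A inhibitors, CYP3A inducers and digoxin. It does not name them either.
- Eligibility and medical history are marked at visit 1 only in Table 2, and the visit 2 timeline has no recheck.
- The section on unblinding refers to decisions on each subject's evaluability before the code is broken, but gives no criterion for interim drug use.

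None of these would detect use that the patient does not report.

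**3. Are the stated purposes met on the dosing day?**

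- Safety: met for benzodiazepines; not met for opiates, and so not for the pain-medicine example.
- Validity (finding denied use): met for benzodiazepines; not met for the other four classes.

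**4. Scale**

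The design has 6 patients per group, 12 in all. One affected patient is 1/6 = 16.7% of an arm, or 1/12 = 8.3% of the trial. The documents give no rate of drug use between the visits and no size for the effect of any class on the CO₂ response, so the calculation stops here.

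**5. Room for the change at visit 2**

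Arrival to capsule is 130 − 120 = 10 minutes. The study code, which is linked to the random assignment, is issued on arrival at visit 2. Planned recruitment is 1 to 2 patients a month for 8 months, that is 8 to 16 patients, against 12 needed.

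**The case against.** The strongest case on the other side is that the schedule is deliberate and consistent with the text. The exclusion is worded as a positive test and not as use, and the description of the screening visit places the toxicology screen there, as Table 2 does. The note's heading separates toxicology tests from benzodiazepine screening, and a dosing-day benzodiazepine test is a plausible check on the two-week restriction on psychiatric medication. Much of this stands. A reader might infer that an interim user meets the exclusion and is then dosed and analysed as eligible in breach of it. The documents do not support that: a patient with no positive test does not meet the criterion as written. A patient who discloses use could be handled through the provision for borderline cases, and evaluability is decided before unblinding. These routes do not reach undisclosed use, which is the case the note says screening is for.

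A reader might also take the note's reference to denied use as a second, narrower exclusion rule. It describes a purpose of testing. It does not say that patients who admit use are accepted, and it needs no edit.

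On safety, a coordinator is in the room from dosing, patients may not drive home, and a companion stays for the remainder of seven hours after the dose. These measures reduce the consequences of additive sedation; they do not detect use or protect the data.

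On size, these patients have just passed a five-class screen and have had no substance use disorder in the six months before screening, so interim use may be uncommon. Amphetamines and cocaine are not sedatives, so the sedation argument does not extend to them.

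**Conclusion.** The point holds as a mismatch between the stated purposes of urine screening and the test scheduled on the dosing day. Undisclosed use of an opiate, cannabinoid, amphetamine or cocaine in the week between visits would go undetected by the scheduled tests. For opiates, the protocol's own pain-medicine safety purpose is not met when the capsule is given.

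A reader might go further and infer a calculable bias in the pilot's effect size. The documents do not support that. Any probability of an affected patient, or any shift in the response, would rest wholly on assumed rates and effects. What can be said is that one patient is 1/6 of an arm, so a single case would carry weight in the estimate.

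The conclusion assumes that Table 2 is complete as to urine testing and that the visit 2 test covers only the class it names. The opening pages were not available and could not be checked.

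**What to change.** Reconcile Table 2 with the exclusion list and its note:

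- In Table 2, replace the benzodiazepine-only urine test at visit 2 with the same five-class panel used at visit 1, run on the urine already required that day.
- In the visit 2 timeline, show the test as a step that is read before the study code and capsule are issued, so that a patient found ineligible on the day does not use up a randomisation code.
- In the note, state which classes are tested at which visit.

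The cost is 12 multi-class tests in place of 12 single-class tests. The pre-dose step would be slightly longer than the 10 minutes now shown, and the reading time for the panel should be checked against that window. An occasional patient may be ineligible on the day and need replacing, which matters somewhat when planned recruitment is 8 to 16 patients for 12 places. No extra visit or staff is needed.

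If the benzodiazepine-only test is intended, the note should say so, give the reason, and say how its pain-medicine purpose is met on the dosing day.
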